#### (2) Selection of research subjects:

This project is a real-world study, including retrospective training, validation and testing cohorts and prospective testing cohorts, all registries are derived from real cases in clinical practice, and the collected case data should include the following requirements:

1. Unresectable hepatocellular carcinoma confirmed by histopathological diagnosis and/or clinical diagnosis (typical imaging features, clinical manifestations, laboratory tests, etc.) (Annex: Guidelines for the diagnosis and treatment of primary liver cancer (2024 edition));
2. Patients who receive TACE combined with targeted immunotherapy on the basis of the diagnosis of unresectable hepatocellular carcinoma;
3. Liver function grade Child-Pugh A or B;
4. Over 18 years old, regardless of gender;
5. Expected survival time  $\geq$  3 months;
6. ECOG PS score  $\leq 2$ ;

7. Meet the following laboratory examination parameters;

- 1) Hematologic function: absolute neutrophil count  $\geq 1.0 \times 10^9 / \text{L}$ ; Platelet count  $\geq 50 \times 10^9 / \text{L}$ ; hemoglobin  $\geq 90 \text{ g/L}$ ; The international normalized ratio is less than 1.7 or the prothrombin time is prolonged by no more than 4 seconds,
- 2) Liver function: alanine aminotransferase/aspartate aminotransferase does not exceed 5 times the upper limit of normal; total bilirubin  $\leq 210 \text{ micromol/L} [\leq 2.38 \text{ mg/dL}]$ ; Albumin  $\geq 28 \text{ g/L}$ ,
- 3) Renal function: serum creatinine does not exceed 1.5 times the upper limit of normal.

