#### **Exclusion Criteria:**

This project is a real-world study, including retrospective training, validation, and testing cohorts and prospective testing cohorts. All registries are derived from real cases in clinical practice, and the collected case data should include the following requirements:

1. At the same time, other malignant tumors except HCC were combined;
2. Moderate to severe ascites (ascites on a Child-Pugh score of 3);
3. Received other first-line or second- and third-line systemic therapy (including any regimen of systemic therapy, etc.) or any local therapy (including transcatheter interventional therapy, ablation therapy, internal/external radiotherapy, etc.) and surgical resection or Chinese herbal medicine within 4 weeks prior to TACE combined with targeted immunotherapy.
4. Incomplete data, such as incomplete baseline laboratory examination data, missing or poor quality imaging data, no prognosis information, etc.;
5. Severe liver dysfunction: liver diseases such as decompensated cirrhosis that seriously affect bilirubin levels;
6. Severe comorbidities: such as refractory hypertension (blood pressure is still higher than 150/100 mm Hg after optimal drug therapy), sustained arrhythmia (CTCAE standard grade 2 and above), atrial fibrillation of any degree, Qtc interval prolongation (more than 450 msec in men and more than 470 msec in women), renal insufficiency, etc.;
7. Concomitant human immunodeficiency virus infection (HIV) or acquired immunodeficiency disorder syndrome;
8. pregnant or lactating women;
9. Accompanied by acute or chronic mental disorders (including mental disorders that affect the enrollment, treatment intervention, and follow-up of subjects).

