### **3. Research Methodology**

This study is based on a multicenter retrospective cohort including a prospective test cohort to include patients with unresectable hepatocellular carcinoma who have received TACE in combination with target-immune therapy. The data comes from the clinical diagnosis and treatment records of 8 tertiary hospitals from 2016 to 2025, and strictly follows the preset inclusion standards.

Generative model construction: diffusion model-based treatment response simulator: input data: enhanced CT/MRI images at the patient's baseline, real post-treatment enhanced CT/MRI images and clinical features (Child-Pugh score, AFP level, treatment plan, etc.). Model architecture: The conditional diffusion model was used to dynamically simulate the virtual follow-up images of the best response after treatment with the treatment protocol (TACE embolic agent dose + target immune drug combination) as the generation conditions. Training mechanism: The model is optimized by comparing the differences in deep visual features between the generated images and the real follow-up images to ensure that the generated results conform to the laws of biological evolution. Quantitatively evaluate the visual fidelity of the generated images (FID index <25); The clinical rationality was scored by 3 interventional radiology experts by blind (on a 5-point scale  $\geq$  4 points were considered qualified).

Dynamic survival prediction framework: Capture 256-dimensional semantic feature vectors from the generated virtual images to characterize the dynamic changes of tumor microenvironment. The depth features extracted by the generative model are fused with the patient's clinical variables, and the key predictors are automatically identified through the gated attention mechanism. Survival risk modeling: Construct a Transformer-based time-series survival model to output individualized survival curves and survival probability predictions at key time points (12/24/36 months).

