## **6. Research plan and forecast progress**

2025/6-2025/12: Complete the collection, cleaning, and statistical analysis of patients' baseline images, efficacy evaluation, and safety data;

2026/01-2026/06: Complete the construction of the generative model, and evaluate and predict the performance of the model;

2025/06-2026/12: Write a research paper and submit it, and complete the final report.

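### The total bilirubin inclusion limit is printed in two units that differ about 5.2-fold, and nothing in the available protocol text says which figure applies

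*Protocol*

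**What the plan says.** In the Protocol, section (2) Selection of research subjects, item 7 is a mandatory laboratory requirement ("Meet the following laboratory examination parameters"). Its liver function line sets the total bilirubin ceiling as "\leq 210 \text{ micromol/L} [\leq 2.38 \text{ mg/dL". It is the only limit in item 7 that carries a second unit in brackets.

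The opening paragraph of the same section says the study covers several cohorts, "including retrospective training, validation and testing cohorts and prospective testing cohorts", and the criteria apply to all of them. Section 3, Research Methodology, says the data come from "8 tertiary hospitals from 2016 to 2025, and strictly follows the preset inclusion standards".

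Two other criteria bear on liver function, and neither gives a bilirubin number:
- Inclusion item 3: "Liver function grade Child-Pugh A or B".
- Exclusion item 5: "Severe liver dysfunction: liver diseases such as decompensated cirrhosis that seriously affect bilirubin levels".

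**The concern.** A second unit in brackets is normally a conversion of the first. Here the two figures are too far apart to be the same limit, so the criterion has two values. If the bracket is a faulty conversion, 210 micromol/L applies. If the lead figure is the faulty one, or if both ceilings are meant to hold, the mg/dL figure decides. The protocol does not choose.

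What is at stake is the definition of the study population. Abstractors reading the same line in different units could admit different patients. If hospitals or cohorts diverged in this way, case mix would differ between the data used to build the model and the data used to test it, and calibration could differ with it. Nothing in the protocol shows that this has happened. Even if everyone uses the same figure, the protocol misdescribes the population in the other unit, and a reader could not reproduce the cohort.

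The protocol itself treats liver function as important. Its justification section links differences in efficacy to it, and section 3 makes the Child-Pugh score an input to the generative model.

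**Working it through.** **Inputs**
- Limit in micromol/L: 210 (Protocol, section (2), item 7, liver function line).
- Limit in mg/dL: 2.38 (same line, in brackets).
- Conversion factor F for bilirubin: 17.1 micromol/L per mg/dL. This is not in the protocol and is an assumption, fixed by a molar mass of about 584.7 g/mol (10000/584.7 = 17.1). Range tried: 17.0 to 17.2.

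**Step 1: try to reproduce the bracketed figure.** mg/dL = (micromol/L)/F, so 210/17.1 = 12.28 mg/dL. The printed 2.38 is not reproduced.

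**Step 2: convert the other way.** micromol/L = (mg/dL) × F, so 2.38 × 17.1 = 40.70 micromol/L. The printed 210 is not reproduced.

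**Step 3: size of the discrepancy over the range of F**

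| F | 210 micromol/L in mg/dL | 2.38 mg/dL in micromol/L | Ratio of limits | Stricter as % of wider |
|---|---|---|---|---|
| 17.0 | 12.35 | 40.46 | 5.19 | 19.3% |
| 17.1 | 12.28 | 40.70 | 5.16 | 19.4% |
| 17.2 | 12.21 | 40.94 | 5.13 | 19.5% |

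At F = 17.1 the disputed range is 210 − 40.70 = 169.3 micromol/L wide, or 12.28 − 2.38 = 9.90 mg/dL.

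**Step 4: can rounding explain it?** Reading 210 as 209.5 to 210.5 and 2.38 as 2.375 to 2.385:
- lowest ratio: 209.5/(2.385 × 17.2) = 5.11
- highest ratio: 210.5/(2.375 × 17.0) = 5.21

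Reading 210 more loosely, as 205 to 215, widens this only to 5.00 to 5.33. The ratio never approaches 1.

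**Step 5: can a slip explain it?** The two figures would agree only with a factor of 210/2.38 = 88.2, about five times bilirubin's. A misplaced decimal point does not help: 21.0/17.1 = 1.23 mg/dL. A factor of 88.2 implies a molar mass of 10000/88.2 ≈ 113 g/mol, which is close to creatinine's usual factor of about 88.4 (210/88.4 = 2.38). Another analyte's conversion may therefore have been used. That is an inference from a constant outside the protocol, the finding does not rest on it, and it does not show which figure was intended.

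**Step 6: does another criterion settle it?** Exclusion item 5 mentions bilirubin only in words, and the Child-Pugh criterion prints no cut-off. Neither selects between the two figures.

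**The case against.** The arithmetic is hard to contest, so the case on the other side is about weight.

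- **The list suggests a lead unit.** The other concentrations in item 7 (neutrophils, platelets, hemoglobin, albumin) are all per litre, and mg/dL appears only in a bracket. An abstractor would probably work from the micromol/L figure. This is fair, and it makes divergence between hospitals less likely. It does not show that the lead figure is the correct one.
- **The practical range is narrower than 41 to 210 micromol/L.** Child-Pugh class, albumin, clotting, transaminases, ascites and the severe liver dysfunction exclusion all apply at the same time. This stands. The raw width does not measure how many patients are affected.
- **Compliance is not wholly undeterminable.** A case at or below about 41 micromol/L meets both figures, and one above 210 fails both. This also stands: only cases in between are undetermined.
- **No analytic harm is shown.** The limit enters no sample size input, performance measure or decision rule, and the study selects records without assigning treatment. One could call this a one-line correction of moderate priority. The point has force on consequence, but a binding eligibility limit that contradicts itself still has to be corrected before it can be applied.
- **The text might have been misread from the PDF.** A lost leading digit (12.38 mg/dL × 17.1 = 211.7 micromol/L) would bring the two close. This cannot be fully excluded, but the neighbouring figures read cleanly and nothing in the line points to a loss.

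**Conclusion.** The point holds and must be fixed. The protocol states one mandatory bilirubin ceiling as two values whose ratio is 5.16 (5.13 to 5.19 for conversion factors of 17.2 to 17.0). The stricter value is about 19% of the wider one. At least one figure is wrong, and nothing in the available text resolves which. The only outside input is the bilirubin conversion factor, and no plausible value of it changes the conclusion.

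The severity rests on the contradiction in an eligibility limit that governs every cohort. The number of cases affected is unknown, and no effect on the C-index or calibration is claimed.

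**What to change.** The sponsor should reconcile the two figures into a single total bilirubin limit, derive the other unit with the bilirubin conversion, and state that the same limit applies in all 8 hospitals and all cohorts. No view is taken here on which value is right.

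The correction should be made before model building begins (section 6: "2026/01-2026/06: Complete the construction of the generative model"). Data collection is scheduled earlier, from June to December 2025, so the correction also needs a re-check of:
- cases already abstracted, against the reconciled limit;
- any cases screened out on bilirubin, where there are such cases.

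The number changing eligibility in each direction should be reported.

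**Cost:** one corrected line and a check of baseline laboratory values already collected. If cases were screened out under the stricter figure and the wider one is adopted, some return to source records and images would be needed, because the protocol does not say that data on screened-out cases are kept.

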#### **Exclusion Criteria:**

This project is a real-world study, including retrospective training, validation, and testing cohorts and prospective testing cohorts. All registries are derived from real cases in clinical practice, and the collected case data should include the following requirements:

1. At the same time, other malignant tumors except HCC were combined;
2. Moderate to severe ascites (ascites on a Child-Pugh score of 3);
3. Received other first-line or second- and third-line systemic therapy (including any regimen of systemic therapy, etc.) or any local therapy (including transcatheter interventional therapy, ablation therapy, internal/external radiotherapy, etc.) and surgical resection or Chinese herbal medicine within 4 weeks prior to TACE combined with targeted immunotherapy.
4. Incomplete data, such as incomplete baseline laboratory examination data, missing or poor quality imaging data, no prognosis information, etc.;
5. Severe liver dysfunction: liver diseases such as decompensated cirrhosis that seriously affect bilirubin levels;
6. Severe comorbidities: such as refractory hypertension (blood pressure is still higher than 150/100 mm Hg after optimal drug therapy), sustained arrhythmia (CTCAE standard grade 2 and above), atrial fibrillation of any degree, Qtc interval prolongation (more than 450 msec in men and more than 470 msec in women), renal insufficiency, etc.;
7. Concomitant human immunodeficiency virus infection (HIV) or acquired immunodeficiency disorder syndrome;
8. pregnant or lactating women;
9. Accompanied by acute or chronic mental disorders (including mental disorders that affect the enrollment, treatment intervention, and follow-up of subjects).

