(3) The models are mostly constructed based on the baseline status of patients, ignoring the dynamic changes of tumor burden and immune landscape in the treatment cycle, which is difficult to guide treatment adjustment in real time and does not meet the needs of precision medicine. Although the traditional longitudinal prediction model can incorporate dynamic changes, it needs to systematically collect follow-up data for multiple visits. In the real world, patient follow-up is often irregular, and there are medical referrals and referrals in other places, resulting in a large number of missing or uneven longitudinal imaging data, and it is difficult to align the information obtained at different time points and different devices. In addition, such models wait for patients to respond to treatment, which has a prediction lag. The LILAC system (Learning-based Inference of Longitudinal imAge Changes) represents an important breakthrough in this direction, which uses a self-supervised time-series deep learning algorithm to analyze small changes in a series of MRI scans to achieve dynamic monitoring of disease progression. The proof-of-concept study showed that LILAC was significantly superior to the traditional method in the prediction of embryonic development time sequence and geriatric cognitive score. In pediatric glioma studies, the time-series deep learning model improved the F1-score of 1-year recurrence prediction by 58.5% by analyzing serial postoperative MRI images, and the prediction performance increased with the increase of historical scans (plateau after 3-6 scans). However, the clinical translation of longitudinal models faces fundamental difficulties: patients with advanced HCC are often unable to complete the full process of imaging follow-up due to disease progression or adverse reactions, resulting in a lack of high-quality time series data; Data heterogeneity is caused by differences in image acquisition protocols in different centers. Ethics and privacy concerns limit multi-center data sharing. Therefore, there is an urgent need to develop new prediction paradigms that do not rely on real post-treatment images. Breakthroughs in Generative Artificial Intelligence provide a revolutionary solution to this.

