## **2. The entry point and significance of this study**

The entry point of this study is to propose "generative longitudinal prediction": only pre-treatment images are needed to generate high-fidelity post-treatment image predictions, which effectively avoids the clinical dilemma of obtaining real longitudinal follow-up data. This paradigm shift not only solves the problem of longitudinal data scarcity, but also develops a new approach to treatment simulation based on digital twins. Clinicians can intuitively evaluate the possible efficacy of different regimens through the virtual multi-time point images generated by the model before treatment, providing a visual basis for individualized treatment decisions. This study integrates generative AI and dynamic risk models to achieve: 1. From static assessment to dynamic deduction; 2. Survival prediction is moved forward; 3. Individualized optimization of treatment plan. It is expected that we can provide more accurate and individualized treatment decision support for patients with advanced liver cancer without relying on longitudinal data, and ultimately improve the survival prognosis and quality of life.

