#### **(3) Sample size:**

Sample size estimation based on the core principles of predictive model development (TRIPOD statement). The core strategy follows an outcome event-driven approach, focusing on the number of target events (e.g., disease positivity). Using the method recommended by Riley et al., the minimum sample size was calculated by the R language pmsampsize package. The calculation parameters include: (1) expected model discrimination (e.g., AUC is preset to 0.8);(2) the estimated number of predictors in the final model (k according to the literature and pre-experiments); and (3) the expected effect strength of the predictor (conservative estimates). At the same time, considering the high-dimensional characteristics of radiomics, the total sample size meets the following empirical criteria: (1) the number of events  $\geq$  (10 times k (EPV principle); (2) Total sample size  $\geq$  (10 times k). The final sample size was increased by 10-20% to compensate for missing data and heterogeneity. Multicenter image heterogeneity was included in the sample size calculation, and the sample size adequacy was verified by Bootstrap sampling.

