Treatment decision support systems: causal effects deduction: quantifying the expected survival benefit of different treatment regimens (eg, TACE + lenvatinib + pembrolizumab versus TACE + bevacizumab + atezolizumab) using a counterfactual analysis framework. Generate a heat map of treatment regimen comparisons to visualize simulated tumor regression differences. Decision rule: When the median survival benefit of a regimen is expected to be more than 3 months and the confidence probability is greater than 80%, the system preferentially recommends the regimen.

Model validation strategy: Stratified by study center, randomly assigned to the training set (70%), validation set (30%), and multiple test sets.

Survival prediction assessment: main indicators: C-index evaluation of overall survival prediction

accuracy; Secondary indicators: 12/24/36 months of time dependence on AUC to assess discriminant ability at a specific time point; Calibration analysis: The Brier score quantifies the prediction error, and the calibration curve evaluates the risk prediction consistency. Comparative experimental design: baseline model (clinical variables only); benchmark model + real follow-up images; Datum model + generate model virtual image.

Reproducibility & Ethics: The model code and preprocessing process are published in the public repository (GitHub). The self-service resampling method (1000 times) was used to calculate the 95% confidence interval.

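### Exclusion 4 makes data completeness an entry rule for the test cohorts too, and its imaging clause can remove poor-prognosis patients and poor-quality scans from the sets used to show performance

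*Protocol*

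**What the plan says.** Item 4 of the Exclusion Criteria (Protocol) removes patients with "Incomplete data, such as incomplete baseline laboratory examination data, missing or poor quality imaging data, no prognosis information, etc". The list is open-ended. It sets no threshold for incomplete or for poor quality, and it does not say whether the imaging clause means baseline images, follow-up images or both. The sentence introducing the list describes the project as "including retrospective training, validation, and testing cohorts and prospective testing cohorts", and no cohort is exempted.

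Three other places bear on this:

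- The background section (Current status and challenges) says that irregular follow-up and care at other sites are common, "resulting in a large number of missing or uneven longitudinal imaging data". It adds that "patients with advanced HCC are often unable to complete the full process of imaging follow-up due to disease progression or adverse reactions".
- The section on the entry point and significance of the study presents the tool as support for patients with advanced liver cancer "without relying on longitudinal data".
- Section (3), Sample size, states: "The final sample size was increased by 10-20% to compensate for missing data and heterogeneity".

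The main survival measure in Research Methodology is "C-index evaluation of overall survival prediction" accuracy, supported by AUC at 12, 24 and 36 months, the Brier score and calibration curves. One of the three models compared is the "benchmark model + real follow-up images" model.

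**The concern.** A test cohort should resemble the patients in whom the tool would be used. By the protocol's own account, many of those patients have incomplete follow-up imaging, and part of the reason is that their disease progressed or treatment was poorly tolerated. If missing follow-up images lead to exclusion, the test sets lose patients for a reason tied to the outcome being predicted. If poor-quality scans lead to exclusion, the test sets also lose the images that would show whether the model withstands ordinary multicentre variation, which the background itself lists as an obstacle to clinical use.

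Absence of prognosis information can be known only after follow-up. In the prospective test cohort, that clause therefore lets a patient be removed on information that arises after baseline.

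This is not a detail that an analysis plan can settle later. An eligibility rule acts before analysis, and imputation or sensitivity analyses cannot bring back patients who were never included.

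**Working it through.** The protocol ties no sample size, event count or missingness rate to this rule, so there is no stated figure to reproduce. The check is mainly a comparison of texts.

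**1. Scope.** The lead-in to the exclusion list names training, validation, testing and prospective testing cohorts. Item 4 therefore applies to the test cohorts.

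**2. Link to prognosis.** The background gives progression and adverse reactions as reasons for incomplete imaging follow-up. Item 4 excludes for missing imaging without restriction to baseline. Together, these allow exclusion to depend on outcome. The background speaks only of follow-up imaging, so the link is documented for that part of item 4 and not for baseline laboratory values or baseline scans.

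**3. Which analyses need follow-up images.** The stated input at the time of use is the pre-treatment image. Real post-treatment images are needed to train the generator, to compare generated with real images, and for the comparator model that uses real follow-up images. Testing the clinical-variables model and the virtual-image model for OS does not need them. Excluding all test patients without follow-up images is therefore unnecessary for the main claim.

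**4. The sample size allowance.** An increase of 10% to 20% makes up for a loss of 1 − 1/1.1 = 9.1% to 1 − 1/1.2 = 16.7%. It restores numbers. It does not change who is left, so it does not correct selection.

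**5. What selection could do (assumptions only).** Let f be the share excluded, HR the death hazard of excluded relative to retained patients, and S = 0.75 the retained patients' 12-month survival. None of these is in the protocol. Survival in all patients is (1 − f) × S + f × S^HR, so the retained group overstates it by f × (S − S^HR).

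| f | HR = 1.0 | HR = 1.5 | HR = 2.0 |
|---|---|---|---|
| 10% | 0 | 0.10 × (0.750 − 0.650) = 1.0 point | 0.10 × (0.750 − 0.5625) = 1.9 points |
| 20% | 0 | 2.0 points | 3.75 points |
| 30% | 0 | 3.0 points | 5.6 points |

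The table shows the mechanism for the observed event rate, which bears on calibration. It says nothing about the C-index or AUC. The gap is zero if excluded patients have the same hazard, and it reverses if their hazard is lower.

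**The case against.** The strongest case against the point is that an image-based model must have usable images, that the imaging clause may have been meant for baseline scans only, and that imputation methods and sensitivity analyses usually belong in an analysis plan that is not at hand. The need for a usable baseline image stands, and the fix keeps that exclusion. The baseline-only reading is possible but is not what the text says. The appeal to an analysis plan fails for patients removed at entry.

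Several stronger readings are tempting and are not supported:

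- **That laboratory gaps alone would remove 10% to 40% of patients.** A reader might count ten items, assume each is independently missing in 1% to 5% of patients, and get 1 − (1 − q)^10 = 10% to 40%. Nine of the ten (neutrophils, platelets, haemoglobin, INR or prothrombin time, ALT, AST, bilirubin, albumin, creatinine) are thresholds in inclusion criterion 7 and must be known to confirm eligibility whatever item 4 says. Among the ten, only AFP is left, and its loss is simply q. The rates and the independence are also invented, and tests ordered together tend to be missing together. The figure should not be used, nor should it be set against the 10–20% allowance.
- **That one missing laboratory value removes a patient.** The protocol sets no threshold, so this is only the strictest reading.
- **That patients with partial follow-up are dropped.** The Validity section takes OS to the date last known alive, so on a plain reading they stay in. Where item 4 draws the line is nevertheless unstated.
- **That performance will not carry over, or is overstated.** Neither can be shown from the document. That the model does worse on poor scans is plausible but undocumented.

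**Conclusion.** The point holds in a limited form. Item 4 applies to the test cohorts, is not confined to baseline images, and conflicts with the protocol's own account of why follow-up images are missing and whom the tool is for. Followed as written, it can remove poor-prognosis patients, and it does remove poor-quality scans, from the sets that are meant to show performance. The reported C-index, AUC and calibration would then apply to a selected group.

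The size and direction of any bias cannot be derived from the document. The link to prognosis rests on reading the imaging clause as covering follow-up images, which its wording allows. The laboratory clause is a lesser matter, because it affects only predictors that are not already eligibility criteria. This is a defect that should be corrected. It does not invalidate the study.

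**What to change.** - Limit item 4 to patients with no usable baseline image, and define usable in advance.
- Do not exclude test patients for missing follow-up images. Run the real-follow-up-image comparator and the generated-versus-real image comparison on the subset that has those images, with all models assessed on that same subset for the head-to-head. Training of the generator can likewise use the patients with paired images.
- Impute missing predictors that are not eligibility criteria, for example AFP, with a model fitted in the training set and applied unchanged to the test sets. Do not impute values needed to establish eligibility.
- Keep every patient with any follow-up, with OS censored at the date last known alive, as the Validity section already provides.
- Report test performance with poor-quality but readable scans included, and give a sensitivity analysis that excludes them.
- Report the number of exclusions and the reasons, separately for each cohort.

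The cost is one imputation model, one sensitivity analysis and an exclusion table. Reported performance may be slightly lower.
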